The **working hypotheses** for this project are: **1)** recurrent hypoglycemia, like that seen in subjects with type 1 diabetes and iatrogenic hypoglycemia, will lead to an upregulation of glucose availability for the brain (by increased transport, and/or increased glycogen storage), thereby facilitating maintenance of cerebral metabolism during subsequent episodes of hypoglycemia, and **2)** recurrent hypoglycemia will lead to an increased GABA tone in hypothalamus, thereby suppressing glucose counterregulation during subsequent episodes of hypoglycemia. To address these hypotheses we will examine cerebral metabolism in subjects with type 1 diabetes and hypoglycemia unawareness, as well as in healthy volunteers preconditioned with euglycemia vs. recurrent hypoglycemia to induce HAAF, thereby permitting us to understand the clinical syndrome as well as isolate the effects of recurrent hypoglycemia from those induced by diabetes.

Aim 1: To determine the contribution of increased glucose availability in the brain to HAAF

Specific Aim 1a: To measure kinetic parameters for glucose transport and metabolism in the hypothalamus of subjects with type 1 diabetes and hypoglycemia unawareness and in healthy volunteers preconditioned with euglycemia vs. recurrent hypoglycemia to induce HAAF.

Hypothesis 1a.1: Subjects with type 1 diabetes and hypoglycemia unawareness will have a higher V_{\max} transport than will healthy volunteers preconditioned with euglycemia.

Hypothesis 1a.2: Healthy volunteers will have a higher V_{\max} transport following preconditioning with recurrent hypoglycemia than with euglycemia.

Specific Aim 1b: To measure brain glycogen turnover and content by ^{13}C MRS in healthy volunteers preconditioned with euglycemia vs. recurrent hypoglycemia to induce HAAF.

Hypothesis 1b: Subjects will have higher glycogen content following preconditioning with recurrent hypoglycemia than with euglycemia.

Aim 2: To determine the contribution of increased GABA tone in the hypothalamus to HAAF

Specific Aim 2: To measure euglycemic and hypoglycemic GABA levels in the hypothalamus of subjects with type 1 diabetes and HAAF and in healthy volunteers preconditioned with euglycemia vs. recurrent hypoglycemia to induce HAAF.

Hypothesis 2a: Hypothalamic GABA levels will be lower during hypoglycemia than during euglycemia in both normal controls and patients with type 1 diabetes.

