The mechanisms responsible for the development of HAAF remain uncertain (5). Clearly, upregulated fuel availability to the brain, either in the form of glucose (free or in glycogen reserves) or in the form of alternative fuels, can result in a failure to detect systemic hypoglycemia, the “unawareness” component of HAAF. While there is conflicting data if *global* cerebral glucose transport or metabolism are altered in HAAF (6-8), *regional* alterations seem likely, particularly in the hypothalamus (9; 10), the region that senses systemic glucose and coordinates the counterregulatory response (11). Our prior data using proton magnetic resonance spectroscopy (^1H MRS) demonstrated higher cortical glucose levels in patients with type 1 diabetes and hypoglycemia unawareness than controls at the same plasma glucose levels (12). Subsequently, we found that oxidative glucose consumption in this brain region was not different in patients with type 1 diabetes and hypoglycemia unawareness than controls (13), indicating that the elevated glucose levels we observed were due to increased glucose transport, rather than decreased metabolism, and that such upregulated glucose transport may provide additional fuel to the brain during subsequent episodes of hypoglycemia to maintain normal function, at least for a while. These studies had focused on the occipital cortex due to technical challenges with studying small and deep brain regions such as the hypothalamus. In fact, glucose content and metabolism have not been measured simultaneously in the human hypothalamus before. We have now overcome these challenges associated with acquiring MRS data from the human hypothalamus (14) (Appendix A, Preliminary studies)

[figure not shown]

Figure 1. Working hypotheses shown with a “simplified” model of brain glucose, glycogen and GABA metabolism. The metabolic pools and kinetic parameters that will be measured are shown in boxes. The predicted relative pool sizes are reflected in the box sizes. BBB: blood brain barrier; CMR_{glc} : cerebral metabolic rate of glucose utilization; Pyr: pyruvate; TCA: tricarboxylic acid cycle; Glu: glutamate.

and further developed methodology to estimate kinetic parameters for glucose transport and utilization simultaneously (15) (Appendix B, Preliminary studies). Therefore we are now in a unique position to address the affects of HAAF on glucose transport and metabolism in this brain region critical in CNS regulation of glycemic control.

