By monitoring incorporation of intravenously infused ^{13}C -glucose into glycogen by ^{13}C MRS, we have previously demonstrated increased brain glycogen synthesis following a single episode of moderate hypoglycemia in healthy humans, indicating glycogen supercompensation (18). On the other hand, we found that glycogen content in subjects with type 1 diabetes and hypoglycemia unawareness is not higher than controls (See C.4. Progress Report). We have interpreted these findings to indicate that supercompensated glycogen levels do not contribute to the pathogenesis of HAAF, perhaps because upregulation of glucose transport in these subjects ensures that they do not experience the reduction in brain glucose content necessary to stimulate glycogen supercompensation following the modest levels of hypoglycemia that routinely occur. However, it is also possible that diabetes itself alters brain glycogen metabolism in such a way as to confound the response to recurrent hypoglycemia. Therefore, we intend to examine the impact of recurrent hypoglycemia on brain glycogen metabolism in healthy volunteers without the confounding effects of diabetes. We will monitor ^{13}C -glucose incorporation into glycogen for up to 80 hours with the goal of turning over the entire glycogen pool for which shorter ^{13}C label infusion periods have been insufficient (18; 26). If we find that brain glycogen content is higher after induction of HAAF in normal volunteers, we can conclude that diabetes does alter brain glycogen metabolism in ways independent of recurrent hypoglycemia. If we find that brain glycogen content is the same or lower after induction of HAAF, we can conclude that supercompensated glycogen does not contribute to the development of HAAF.

Research Subjects:

Healthy controls will be recruited from the University of Minnesota community. Exclusion criteria will include history of stroke, seizures, neurosurgical procedures, or arrhythmias, and use of drugs that can alter glucose metabolism. Subjects must also meet requirements for a study in the magnet, which includes weight less than 300 lbs and the absence of metallic substances in their body.

Study Protocol:

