¹³C-glycogen levels in the brain will be measured on a 4 T / 90 cm magnet (Oxford/Varian) using a quadrature 14 cm ¹H surface coil combined with a 9 cm diameter linear ¹³C coil (41). The [1-¹³C]glycogen NMR signal will be localized in a 7 × 5 × 6 cm³ voxel in the occipital lobe as described before (25). The amount of ¹³C label in the C1 position of glycogen will be quantified by the external reference method (23; 24). The [1-¹³C]glycogen concentrations will be divided by the plasma glucose isotopic enrichment (IE) to correct for differences in IEs between subjects and to determine the newly synthesized glycogen concentrations. ¹³C-glycogen levels will be corrected for the cerebrospinal fluid (CSF) content of the voxel (34).

Sample size justification and data analysis plan:

¹³C-glycogen levels will be compared following euglycemic preconditioning to following hypoglycemic conditioning with a repeated measures model with effects for precondition, acquisition time (5, 12, etc. hours), and their interaction; we will also test for an effect of the order of preconditioning. Correlation structures appropriate for doubly-repeated measures (across acquisition times within preconditioning, for two preconditioning sessions) will be used. Previous work (18) shows standard deviations of the group difference ranging from 0.2 to 0.4 μmol/g across the acquisition times, indicating that with 5 participants we will have 85% power to detect paired-group differences between 0.36 and 0.73 μmol/g with type I error of 5%. Per-acquisition-time group comparisons will be adjusted for multiple comparisons using Sidak's method. We have budgeted for 6 participants to allow for one failed study without sacrificing power. Since we have detected highly significant differences during and following single hypoglycemia vs. euglycemia in our prior studies with 5 subjects per group (18), we expect to be able to also detect a difference with 5 subjects who will serve as their own controls, if recurrent hypoglycemia does affect glycogen content/metabolism.

Potential pitfalls and solutions:

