We have had success in recruiting subjects to participate in similar protocols in the past (18; 26) and all of the methods are well established in our laboratory. Thus, we do not anticipate any problems with the completion of the work. As in our previous work (18; 24; 26) glycogen content and turnover will be studied in the occipital lobe because of the low cerebral glycogen concentrations, the large size of the molecule that broadens its MR signal and the resulting small ¹³C MRS signal. It would be ideal to study hypothalamic glycogen levels and turnover; however this is not possible with the currently available technology and no other methods exist to monitor glycogen in the intact human brain.

As for aim 1a, we may find that the protocol we use to induce HAAF will not be effective for all subjects enrolled in the study. To ensure that HAAF is present at the time we examine glycogen metabolism, we will measure counterregulatory hormones in blood collected from subjects during the hypoglycemic clamps. If the epinephrine response (the hormone most blunted during most protocols in which HAAF is induced in humans (30; 31)) during the third hypoglycemic clamp is $\geq 70\%$ of the response measured during the first hypoglycemic clamp, we will conclude that HAAF was not induced and the data will not be used for analysis. If HAAF fails to be induced in 1/3, 2/5, 3/7, 4/9,... of the studies (we will monitor in an ongoing way), we will change the protocol to induce HAAF to include more episodes of hypoglycemia before the glycogen experiment.

Aim 2: To measure euglycemic and hypoglycemic GABA levels in the hypothalamus of subjects with type 1 diabetes and HAAF and in healthy volunteers preconditioned with euglycemia vs. recurrent hypoglycemia to induce HAAF.

In these experiments, subjects with type 1 diabetes and HAAF (as confirmed by counterregulatory hormone measurements during a hypoglycemic clamp), as well as normal controls with and without HAAF, will have hypothalamic GABA levels measured at a blood glucose of 95 mg/dl and again at a glucose level of 50 mg/dl by ¹H MRS at 7 tesla over a ~one hour period.

Study rationale:

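### Aim 1b: finding glycogen content *the same* in an occipital voxel, with 5 or 6 subjects and no margin, cannot show that supercompensated glycogen plays no part in HAAF

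*Combined protocol and SAP*

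**What the plan says.** Aim 1b compares brain glycogen in healthy volunteers after euglycemic and after hypoglycemic preconditioning, each subject serving as their own control. The hypothesis in Specific Aims is directional: "Subjects will have higher glycogen content following preconditioning with recurrent hypoglycemia than with euglycemia".

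The Study rationale for Aim 1b gives a reading for each outcome. For the negative one, if "brain glycogen content is the same or lower after induction of HAAF, we can conclude that supercompensated glycogen does not contribute" to the syndrome. No margin, confidence limit or brain region is attached.

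The analysis section for Aim 1b plans a repeated measures model with preconditioning, acquisition time and their interaction, and Sidak adjustment of the comparisons at each time. The sample size statement takes SDs of 0.2 to 0.4 μmol/g for the difference, "indicating that with 5 participants we will have 85% power to detect paired-group differences between 0.36 and 0.73" μmol/g at a type I error of 5%. It adds: "We have budgeted for 6 participants to allow for one failed study without sacrificing power".

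The ¹³C MRS methods place the voxel in the occipital lobe. The pitfalls section concedes: "It would be ideal to study hypothalamic glycogen levels and turnover; however this is not possible with the currently available technology". Section A describes the hypothalamus as "the region that senses systemic glucose and coordinates the counterregulatory response", and Specific Aims says much the same.

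**The concern.** Two inferences are folded into one sentence. The first runs from no difference found to no difference present. A test designed to detect a difference cannot support that step without a stated margin and an interval narrow enough to meet it. The second runs from the occipital lobe to the whole syndrome, although the protocol assigns glucose sensing and coordination of counterregulation to a region where glycogen cannot be measured.

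Glycogen is one of three mechanisms the project sets out to test, beside glucose and GABA. If the sentence is followed as written, an imprecise null from a handful of subjects would be taken to dismiss one of them.

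**Working it through.** **1. The plan's own figure.** Inputs from the Aim 1b sample size statement: n = 5 paired, SD of the difference 0.2 to 0.4 μmol/g, type I error 5% (sidedness not stated). Power of a two-sided paired t-test comes from the noncentral t distribution with 4 df and noncentrality Δ√n/SD.

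- Δ = 0.36, SD = 0.2: 0.36 × 2.236 / 0.2 = 4.02; power 84.7%.
- Δ = 0.73, SD = 0.4: 0.73 × 2.236 / 0.4 = 4.08; power 85.6%.

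Solving for 85% gives 0.361 and 0.723 μmol/g, so the stated figures reproduce. A one-sided test would give 0.29 to 0.59. The detectable difference is about 1.8 SDs of the paired difference (0.36/0.2 = 1.80; 0.73/0.4 = 1.83).

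**2. What an observed zero leaves open.** The 95% half-width at one acquisition time, unadjusted, is t(0.975, n−1) × SD/√n.

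| n analysed | t | SD 0.2 | SD 0.4 |
|---|---|---|---|
| 4 | 3.182 | 0.32 | 0.64 |
| 5 | 2.776 | 0.25 | 0.50 |
| 6 | 2.571 | 0.21 | 0.42 |

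The row for 4 is shown because subjects in whom HAAF is not induced are dropped, while the budget covers one loss. With Sidak over the eight listed times, the per-comparison level is 1 − 0.95^(1/8) = 0.0064, and the half-width at n = 5 becomes 0.47 to 0.94.

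**3. Illustration only.** Suppose *the same* is read as *not significant*, and the true increase is half the stated detectable difference (0.18 μmol/g at SD 0.2; 0.365 at SD 0.4). Single-time power at n = 5 is 33.9% and 34.7%, so about 65% of such studies would miss it. With 6 subjects about 57% would.

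**4. What could be excluded.** Take a true difference of zero, an upper limit at one-sided 2.5%, and 85% probability that it falls below the margin, again at a single time. The 0.20 margin is an assumption; the other two are the plan's detectable differences.

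| Margin (μmol/g) | n at SD 0.2 | n at SD 0.4 |
|---|---|---|
| 0.73 | 3 | 5 |
| 0.36 | 6 | 14 |
| 0.20 | 12 | 38 |

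At the planned size, only margins near the stated detectable difference are within reach.

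**5. Region.** No arithmetic applies. The voxel is occipital, the methods cannot reach the hypothalamus, and the conclusion names no region. The Aim 1a rationale treats its own earlier occipital glucose findings more cautiously, saying they do not show what recurrent hypoglycemia does in the hypothalamus. The same caution is not carried over to glycogen.

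**The case against.** The sentence is rationale prose, not a rule in the analysis section, and nothing there equates *the same* with a p-value above 0.05. That is fair, and it is why the 65% figure is conditional. But the sentence is the only stated reading of a null result.

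The calculations use one time point, while the plan fits a repeated measures model over eight. This also stands. The pooled preconditioning effect may be more precise, but the documents give no within-subject correlation, so the gain cannot be computed. The Sidak-adjusted comparisons would be less precise. Pooling would supply neither a margin nor hypothalamic data.

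The plan notes that earlier work with 5 subjects per group found highly significant differences around a single hypoglycemic episode. That supports the hope of detecting a large effect. It does not turn a failure to detect one into evidence of absence.

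The occipital restriction is disclosed as a technical limit. Agreed: the choice of voxel is not the fault. The caveat is simply missing from the conclusion.

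A reader might also infer from section A that the protocol expects glycogen changes to be regional. It does not say so. Its remark about conflicting global data and likely regional changes concerns glucose transport or metabolism, and it calls the mechanisms of HAAF uncertain. The regional point here rests only on where sensing and counterregulation are placed and where glycogen is measured.

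**Conclusion.** The concern holds in a limited form. The *same* half of the sentence is unsupported because no margin exists. On the plan's own SDs, an observed zero at one unadjusted time point leaves open an increase of 0.25 to 0.50 μmol/g with 5 subjects, or 0.21 to 0.42 with 6. The *lower* half is defensible within the occipital lobe: an upper confidence limit below zero would exclude supercompensation there. Neither half supports a statement about the hypothalamus.

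Three stronger readings are tempting and should be avoided:

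- That the power calculation is wrong. It reproduces.
- That the plan has a 65% error rate. That figure assumes that *the same* means *not significant*, a single time point, and a true increase of half the detectable difference. The documents give neither total glycogen content nor a smallest important increase, so nothing shows that an increase of that size matters, or that it would prove a contribution to HAAF.
- That glycogen does contribute in the hypothalamus. The design is silent on this either way.

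**What to change.** Replace the negative-outcome sentence in the Aim 1b Study rationale with text such as:

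> We will report the hypoglycemia-minus-euglycemia difference in glycogen content with its 95% confidence interval from the repeated measures model. Where no increase is shown, and the upper limit lies below [one value fixed before analysis: an increase the study was designed to detect, within 0.36 to 0.73 μmol/g, or a smaller one], we will conclude that occipital glycogen is not increased by that amount; otherwise the result is inconclusive. Any null conclusion applies to the occipital lobe only and does not exclude hypothalamic supercompensation.

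The sponsor should put a single number in the bracket and name the contrast it applies to (the pooled preconditioning effect or a stated acquisition time), because their precision will differ. A detectable difference shows what the study can see, not what matters biologically, so the choice needs a sentence of justification.

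No extra subjects, scans or tests are needed. The sponsor gives up the unqualified negative claim. On single-time precision, only increases about as large as the stated detectable difference can be excluded at the planned size, so some null results will have to be reported as inconclusive.

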We will examine the impact of repeated episodes of hypoglycemia on brain glycogen content and turnover in healthy controls. As in Aim 1a, subjects will be studied both after preconditioning with euglycemia and after preconditioning with recurrent hypoglycemia to induce HAAF, done in random order separated by a minimum of 6 weeks (Fig. 6). Female controls will have their two studies two months apart in order to control for phase of menstrual cycle.

The hypoglycemia preconditioning and euglycemia preconditioning protocols will be identical to those described in Aim 1a, with the first MRS session to measure ^{13}C -glycogen level in the afternoon on Day 2 (Fig. 6). At minute +30 following the end of the last hypoglycemic or euglycemic clamp, a bolus injection of 20 g of $[1-^{13}\text{C}]$ glucose (prepared as 20% weight/volume D-glucose in water with 50% isotopic enrichment) will be administered to subjects regardless of their preconditioning protocol. Twenty minutes later a continuous infusion of 2 mg/kg/min of $[1-^{13}\text{C}]$ glucose (prepared as 20% weight/volume D-glucose in water with 25% isotopic enrichment) will be started and then adjusted to maintain blood glucose at ~ 125 mg/dl based on samples collected every 10-60 minutes and measured on an automatic glucose analyzer. The infusion of ^{13}C -glucose will continue for ~ 82 hours. Cerebral ^{13}C -glycogen levels will be measured at $\sim 5, 12, 22, 34, 46, 58,$

70 and 82 hours after the end of the last hypoglycemic or euglycemic clamp. Blood samples will also be frozen for the later determination of plasma insulin concentrations by a chemiluminescent assay (Immulite, Diagnostic Products Corporation, Los Angeles, CA), and of the isotopic enrichment of the plasma glucose by gas-chromatography-mass spectroscopy (GC-MS) as described previously (40).

¹³C MRS methods:

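### Aim 1b's 85% power is for a single unadjusted time point; at the planned Sidak level it is about 35% on the same paired-t basis, and the model's precondition effect has no power statement

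*Combined protocol and SAP*

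**What the plan says.** All places are in section C.2 unless noted.

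- **Hypothesis 1b (Specific Aims):** "Subjects will have higher glycogen content following preconditioning with recurrent hypoglycemia than with euglycemia". No acquisition time is named.
- **Aim 1b, Study Protocol:** glycogen is measured at about 5, 12, 22, 34, 46, 58, "70 and 82 hours after the end of the last hypoglycemic or euglycemic clamp". That is eight times per session.
- **Aim 1b, Sample size justification and data analysis plan:** the analysis is "a repeated measures model with effects for precondition, acquisition time (5, 12, etc. hours), and their interaction", with a test for order and a doubly-repeated correlation structure. Earlier work is said to show "standard deviations of the group difference ranging from 0.2 to 0.4" µmol/g across the times. From this, "with 5 participants we will have 85% power to detect paired-group differences between 0.36 and 0.73" µmol/g at a type I error of 5%. The next sentence reads "Per-acquisition-time group comparisons will be adjusted for multiple comparisons using Sidak's method". Then: "We have budgeted for 6 participants to allow for one failed study without sacrificing power".
- **Aim 1b, Study rationale:** "If we find that brain glycogen content is the same or lower after induction of HAAF", the authors will conclude that supercompensated glycogen plays no part in the development of HAAF.

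The plan does not state the size of the Sidak family, the error degrees of freedom, the correlation between times, or which test decides Hypothesis 1b.

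**The concern.** The power statement uses the SD of the paired difference at individual times and a 5% level, so it describes an unadjusted test at one time. The plan does not intend that test, because its per-time tests are Sidak-adjusted. The other candidate, the model's precondition effect, would need the SD of an average over times, and none is given. The 85% therefore belongs to neither planned analysis, although a reader will take it as the power of the comparisons described.

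This matters most for a null result. The Study rationale commits in advance to reading one as evidence against a role for glycogen. With five people and no interval rule, an imprecise null could be reported as a negative finding, and the 85% would make it look informative.

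**Working it through.** **Inputs.** SD of the paired difference 0.2 to 0.4 µmol/g; n = 5 (6 budgeted); differences 0.36 and 0.73 µmol/g; type I error 5% (all from the Aim 1b sample size section). Eight acquisition times (Aim 1b Study Protocol). Taking these eight as the Sidak family is an assumption.

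**Step 1: reproduce the plan's figure.** Two-sided paired t-test, df = n − 1 = 4, noncentrality = (difference/SD) × √n.

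- 0.36/0.2 = 1.80; × √5 = 4.02; power at alpha 0.05 = 84.7%.
- 0.73/0.4 = 1.825; × √5 = 4.08; power = 85.6%.
- Standardised difference for 85% power = 1.807, so 1.807 × 0.2 = 0.361 and 1.807 × 0.4 = 0.723 µmol/g.

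This matches. Other versions do not: one-sided t gives 0.294/0.588, two-sided normal 0.268/0.536, one-sided normal 0.240/0.480.

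**Step 2: apply the Sidak level.** Alpha per time = 1 − 0.95^(1/8) = 0.00639. With 4 df the critical value rises from 2.78 to 5.23.

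| Evaluable participants | Power at 0.36 (SD 0.2) | Power at 0.73 (SD 0.4) |
|---|---|---|
| 5 | 34.7% | 35.8% |
| 6 | 54.2% | 55.6% |
| 8 | 83.6% | 84.8% |
| 9 | 91.4% | 92.2% |

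Detectable with 85% power:

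- n = 5: standardised difference 3.153, hence 0.63 to 1.26 µmol/g.
- n = 6: standardised difference 2.474, hence 0.49 to 0.99 µmol/g.

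**Step 3: sensitivity to what the plan leaves open (n = 5).**

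- Family size: 69–71% for 2 times, 51–53% for 4, 35–36% for 8.
- Error df, same noncentrality: 64–66% with 8 df, 79–81% with 16, 85–86% with 28. The last is full pooling, (5 − 1) × (8 − 1) = 28. It assumes equal variances, whereas the stated SDs differ twofold.

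**Step 4: the averaged precondition effect.** Assume equal SDs, a common between-time correlation rho, a difference of 1.8 SD, n = 5, alpha 0.05 unadjusted. The SD of the eight-time mean is the single-time SD × √((1 + 7 rho)/8). If the difference is present only at the last four times, the mean difference is 0.9 SD.

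| rho | SD factor | Present at all 8 times | Last 4 only |
|---|---|---|---|
| 0.3 | 0.622 | 99.6% | 68.1% |
| 0.6 | 0.806 | 95.4% | 47.6% |
| 0.9 | 0.955 | 87.6% | 36.5% |

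**Step 5: chance of at least one Sidak-significant time** (simulation; n = 5, 4 df, eight times, 1.8 SD, rho 0.3 to 0.9). It is about 92% falling to 59% if the difference is present at all times, and about 78% falling to 52% if only at the last four.

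**Step 6: precision of a null at one time.** 95% half-width = 2.776 × SD/√5, which is 0.248 for SD 0.2 and 0.497 for SD 0.4 µmol/g.

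**The case against.** The strongest reply is that 35% is a low-end figure and does not describe the aim as a whole. The plan names no power method; the paired t-test is inferred because it reproduces the numbers. The planned comparisons come from a repeated measures model, not eight separate 4-df t-tests, and pooling could lift per-time power as far as 85–86%. Also, 35% is the chance of significance at one given time, while the chance at some time is higher (step 5). The model's precondition effect carries no stated adjustment and would have 88% to over 99% power for a sustained difference. On that reading the Sidak tests are follow-up, and the rationale's remark about a null is background rather than an analysis rule.

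Much of this stands as a limit on scope. The precondition effect is not shown to be underpowered, and 35% must not be read as the chance of finding any effect. The pooled-df point is valid too, but only full pooling recovers 85%, and the plan neither states it nor used it in the calculation that reproduces its figures. The plan does not call the per-time tests secondary, does not claim any-time power, and gives no power for the averaged effect. The remark about a null is in the rationale, but it is the only rule given for interpreting one.

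**Conclusion.** The concern holds. The plan's arithmetic is correct for the test it computes, but that test is not one it plans to use. On the same paired-t basis, per-time power at the Sidak level for eight times is 35–36% with 5 participants and 54–56% with 6, against the stated 85%. The detectable difference is 0.63–1.26 µmol/g against 0.36–0.73, about 1.75 times larger (3.153/1.807).

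These figures assume a family of eight and 4 df. Per-time power stays below 85% for every smaller family examined at 4 df, and reaches 85% only with full pooling. For the precondition effect the defect is a missing statement: its power could be above or well below 85%, depending on when the difference appears and how correlated the times are.

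The null reading adds to the problem. At one time the 95% half-width is 0.25–0.50 µmol/g. At SD 0.2, a null centred on zero would reach 0.25 and so exclude the 0.36 paired with that SD. At SD 0.4 it would reach 0.50, below 0.73 but above 0.36. Whether such a null is informative depends on a margin the plan does not give. This should be fixed.

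**What to change.** Choose one of two routes in the Aim 1b sample size section.

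1. **Restate the per-time power at the Sidak level**, giving the family size and df method. For eight times and the paired-t method: with 5 participants, the adjusted comparison at any one time has about 35% power for 0.36–0.73 µmol/g and 85% power for 0.63–1.26 µmol/g. A different family or df method needs its own figures.
2. **Name one prespecified, unadjusted contrast as the primary test of Hypothesis 1b**, either the model's precondition effect or a late-time average. Attach the 5% level to it, give its power using the SD of that contrast, and label the Sidak-adjusted per-time tests secondary.

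The second route is safer because it does not depend on an unsettled df method.

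Under either route, replace the Study rationale's reading of a null. Conclude that glycogen does not contribute only if the upper 95% limit of the difference in content (hypoglycemic minus euglycemic preconditioning) lies below a margin the investigators state and justify in advance. Otherwise report the result as inconclusive.

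**Cost:** wording only, with no new data. Under route 1 the stated per-time power looks less favourable, and under either route some null results become inconclusive. Keeping an 85% per-time claim at the Sidak level under the paired-t method would need about 9 evaluable participants (8 give 84–85%).
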